CGM System Glucose Ranges (mg/dL)	Number of Paired CGM-YSI	Mean Relative Difference (%)	Median Relative Difference (%)	Mean Absolute Relative Difference (%)	Median Absolute Relative Difference (%)
Overall					
40-60*					
61-80*					
81-180					
181-300					
301-350					
351-400					

*For CGM ≤ 80 mg/dL, the differences in mg/dL are included instead of percent difference (%).

Table 6C. CGM System Agreement to Reference within YSI Glucose Ranges (Sample Table)

YSI Glucose Range (mg/dL)	Number of Paired Eversense™ CGM and YSI Reference	Percent of CGM System Readings Within				
		Percent 15/15% of Reference	Percent 20/20% of Reference	Percent 30/30% of Reference	Percent 40/40% of Reference	Percent Greater than 40/40% of Reference
Overall						
< 40						
40 - 60						
61 - 80						
81 - 180						
181 - 300						
301 - 350						
351 - 400						
> 400						

Table 6D. CGM System Agreement to Reference within CGM System Glucose Ranges (Sample Table)

CGM System Glucose Range (mg/dL)	Number of Paired Eversense™ CGM and YSI Reference	Percent of CGM System Readings Within				
		Percent 15/15% of Reference	Percent 20/20% of Reference	Percent 30/30% of Reference	Percent 40/40% of Reference	Percent Greater than 40/40% of Reference
Overall						
40 - 60						
61 - 80						
81 - 180						
181 - 300						
301 - 350						
351 - 400						

Table 7A. Concurrence of CGM System Readings and YSI Values within YSI Glucose Ranges (Sample Table)

YSI (mg/dL)	Number of Paired CGM-YSI (n)	Percent of Matched Pairs in Each CGM System Glucose Range for Each YSI Glucose Range									
		CGM (mg/dL)	40-60	61-80	81-120	121-160	161-200	201-250	251-300	301-350	351-400
<40											
40-60											
61-80											
81-120											
121-160											
161-200											
201-250											
251-300											
301-350											
351-400											
>400											

Table 7B. Concurrence of CGM System Readings and YSI Values within CGM System Ranges (Sample Table)

CGM (mg/dL)	Number of Paired CGM-YSI (n)	Percent of Matched Pairs in Each YSI Glucose Range for Each CGM Glucose Range YSI (mg/dL)										
		<40	40-60	61-80	81-120	121-160	161-200	201-250	251-300	301-350	351-400	>400
40-60												
61-80												
81-120												
121-160												
161-200												
201-250												

CGM (mg/dL)	Number of Paired CGM-YI (n)	Percent of Matched Pairs in Each YSI Glucose Range for Each CGM Glucose Range YSI (mg/dL)									

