4.1 Study Objectives

4.1.1 Effectiveness

The effectiveness objective is to determine the accuracy of the Senseonics CGM System through 90 days post-insertion for reference glucose values from 40-400 mg/dL. The exploratory objectives are to determine other relevant Senseonics CGM System performance measures during the period of Sensor use and are detailed further in Section 6, along with plans and analysis details on the effectiveness endpoint. An interim analysis will be performed and data submission will be made based on the sensor performance data accrued through the day 30 visit (Visit 6).

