4.2 Endpoints

4.2.1 Effectiveness Endpoint

The effectiveness objective is to descriptively document the distribution of absolute relative difference across all subjects and to estimate the MARD. The MARD will be estimated initially when all the subjects complete 30 days of Sensor use for the interim analysis, followed by the MARD based on all the follow-up data through 90 days of Sensor use.

The effectiveness endpoint will be calculated for three different combinations of 2 generations of hardware and 2 generations of firmware. The three configurations are Generation 1 (Gen 1)

transmitter plus study firmware, Generation 2 (Gen 2) transmitter plus study firmware and Gen 2 transmitter plus updated firmware.

Descriptive statistics will be provided for the MARD and other exploratory effectiveness endpoints. There is no hypothesis to be tested. No inferential statistical analysis will be performed.

The effectiveness endpoint is the mean absolute relative difference (MARD), defined as the average of absolute difference of paired Senseonics CGM System and reference glucose readings divided by the reference glucose reading (reference) for all reference glucose values, that is:

$$\text{MARD} = \left(\left(\sum \frac{|(\text{Glucose})_{\text{SENSOR}} - (\text{Glucose})_{\text{REFERENCE}}|}{(\text{Glucose})_{\text{REFERENCE}}} \right) / n \right) \times 100\%$$

Where, n is the total number of CGM and reference glucose pairs during the evaluation period, that is, after 30 days of Sensor use for the interim analysis, and after 90 days of use.

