6.3 Data for Analysis

All data will be used for the study safety and effectiveness analysis.

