6.4 Analysis Populations

Effectiveness Analysis population: The effectiveness analysis and exploratory effectiveness endpoints will be based on all data from all subjects in this investigation with at least one paired glucose reading (one Sensor with one reference glucose). The Senseonics CGM System and reference readings are compared by pairing each reference reading with the first Sensor reading that occurred up to 5 minutes after sample acquisition.

Safety Analysis Population: Safety analysis will be based on all subjects that undergo the sensor insertion in this investigation.

Dexamethasone Analysis Population: The approximately 6 to 9 subjects with Sensor's inserted will constitute the dexamethasone analysis population to determine if and when a peak dexamethasone level occurs. Subsequent to determining if and when a peak occurs, all subjects with Sensor's inserted will constitute the complete dexamethasone analysis population.

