6.10.1.7 Effect of compression on sensor performance during sleep challenges

For the sleep assessment periods during visits 4 & 5, compression may occur to the sensor site when the subject is sleeping at night. The system's difference and agreement with reference and between system precision will be compared between the night time and the day time (Tables 10A and 10B in APPENDIX 1).

6.10.1.8 Mean Absolute Difference between sensor and reference measurements for reference values less than or equal to 80mg/dL

The mean absolute difference (MAD) for reference glucose values less than or equal to 80 mg/dL is defined as the absolute difference of paired Senseonics CGM System and Reference readings for reference glucose values ≤ 80 mg/dL.

$$MAD = \left(\sum |(Glucose)_{SENSOR} - (Glucose)_{REFERENCE}| \right) / n$$

This analysis will quantify both cumulative results as well as stability over time in 30 day intervals (Tables 11A and 11B in APPENDIX 1).

6.10.1.9 Mean Absolute Difference between sensor and reference measurements for system full scale range (40-400mg/dL)

$$MAD = \left(\sum |(Glucose)_{SENSOR} - (Glucose)_{REFERENCE}| \right) / n$$

This analysis will quantify both cumulative results as well as stability over time in 30 day intervals (Tables 11A and 11B in APPENDIX 1).

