		40-60	61-80	81-120	121- 160	161- 200	201- 250	251- 300	301- 350	351-400
<40										
40-60										
61-80										
81-120										
121-160										
161-200										
201-250										
251-300										
301-350										
351-400										
>400										

Table 2.7. Concurrence of CGM System Readings and YSI Values within CGM System Ranges (Sample Table)
Table 2.7A

CGM (mg/dL)	Number of Paired CGM-YSI (n)	Gen 1 Tx (Study FW) Percent of Matched Pairs in Each YSI Glucose Range for Each CGM Glucose Range YSI (mg/dL)									
		<40	40-60	61-80	81-120	121- 160	161- 200	201- 250	251- 300	301- 350	351- 400
40-60											
61-80											
81-120											
121-160											

CGM (mg/dL)	Number of Paired CGM-YSI (n)	Gen 1 Tx (Study FW)									
		<40	40-60	61-80	81-120	121- 160	161- 200	201- 250	251- 300	301- 350	351- 400
161-200											
201-250											
251-300											
301-350											
351-400											

Table 2.7B

CGM (mg/dL)	Number of Paired CGM-YSI (n)	Gen 2 Tx (Study FW)									
		<40	40-60	61-80	81-120	121- 160	161- 200	201- 250	251- 300	301- 350	351- 400
40-60											
61-80											
81-120											
121-160											
161-200											
201-250											
251-300											
301-350											
351-400											

Table 2.7C

CGM (mg/dL)	Number of Paired CGM-YSI (n)	Gen 2 Tx (Updated FW)									
		<40	40-60	61-80	81-120	121- 160	161- 200	201- 250	251- 300	301- 350	351- 400
40-60											
61-80											
81-120											
121-160											
161-200											
201-250											
251-300											
301-350											
351-400											

Table 2.8. CGM System Accuracy by Visit Number (Sample Table)
Table 2.8A

Percent of CGM System Readings within 15/15%				
YSI Glucose Range (mg/dL)	Number of Points	Hardware Version (Firmware Version)		
		Gen 1 Tx (Study FW)	Gen 2 Tx (Study FW)	Gen 2 Tx (Updated FW)
Day 1				

Overall				
<40	TBD	TBD	TBD	TBD
40-60	TBD	TBD	TBD	TBD
61-80	TBD	TBD	TBD	TBD
81-180	TBD	TBD	TBD	TBD
181-300	TBD	TBD	TBD	TBD
301-350	TBD	TBD	TBD	TBD
351-400	TBD	TBD	TBD	TBD
>400	TBD	TBD	TBD	TBD

Day 7

Overall				
<40	TBD	TBD	TBD	TBD
40-60	TBD	TBD	TBD	TBD
61-80	TBD	TBD	TBD	TBD
81-180	TBD	TBD	TBD	TBD
181-300	TBD	TBD	TBD	TBD
301-350	TBD	TBD	TBD	TBD
351-400	TBD	TBD	TBD	TBD
>400	TBD	TBD	TBD	TBD

Day 14

Overall				
<40	TBD	TBD	TBD	TBD
40-60	TBD	TBD	TBD	TBD
61-80	TBD	TBD	TBD	TBD
81-180	TBD	TBD	TBD	TBD
181-300	TBD	TBD	TBD	TBD
301-350	TBD	TBD	TBD	TBD
351-400	TBD	TBD	TBD	TBD
>400	TBD	TBD	TBD	TBD

Day 30

Overall				

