61-80	TBD	TBD	TBD	TBD
81-180	TBD	TBD	TBD	TBD
181-300	TBD	TBD	TBD	TBD
301-350	TBD	TBD	TBD	TBD
351-400	TBD	TBD	TBD	TBD
>400	TBD	TBD	TBD	TBD
Day 7				
Overall				
<40	TBD	TBD	TBD	TBD
40-60	TBD	TBD	TBD	TBD
61-80	TBD	TBD	TBD	TBD
81-180	TBD	TBD	TBD	TBD
181-300	TBD	TBD	TBD	TBD
301-350	TBD	TBD	TBD	TBD
351-400	TBD	TBD	TBD	TBD
>400	TBD	TBD	TBD	TBD
Day 14				
Overall				
<40	TBD	TBD	TBD	TBD
40-60	TBD	TBD	TBD	TBD
61-80	TBD	TBD	TBD	TBD
81-180	TBD	TBD	TBD	TBD
181-300	TBD	TBD	TBD	TBD
301-350	TBD	TBD	TBD	TBD
351-400	TBD	TBD	TBD	TBD
>400	TBD	TBD	TBD	TBD
Day 30				
Overall				
<40	TBD	TBD	TBD	TBD
40-60	TBD	TBD	TBD	TBD
61-80	TBD	TBD	TBD	TBD
81-180	TBD	TBD	TBD	TBD
181-300	TBD	TBD	TBD	TBD
301-350	TBD	TBD	TBD	TBD
351-400	TBD	TBD	TBD	TBD
>400	TBD	TBD	TBD	TBD

Table 2.9. System Reliability

System Reliability	Transmitter Version	
	Gen 1 Tx (Study FW)	Gen 2 Tx (Study FW)
Matched CGM-YSI Pairs	TBD*	TBD *
Number of Sensors Logging Data with Transmitter	TBD	TBD
Mean Number of Matched Pairs Per Sensor	TBD	TBD

* Does not include data when the Systems displays High or Low Glucose

Table 2.10. CGM System Performance during Sleep Challenges (Sample Table)

During Night	Hardware Version (Firmware Version)			During Day	Hardware Version (Firmware Version)		
	Gen 1 Tx (Study FW)	Gen 2 Tx (Study FW)	Gen 2 Tx (Updated FW)		Gen 1 Tx (Study FW)	Gen 2 Tx (Study FW)	Gen 2 Tx (Updated FW)
Mean Absolute Relative Difference (%)	TBD	TBD	TBD	Mean Absolute Relative Difference (%)	TBD	TBD	TBD
Median Absolute Relative Difference (%)	TBD	TBD	TBD	Median Absolute Relative Difference (%)	TBD	TBD	TBD
15/15%				15/15%			
20/20%				20/20%			
30/30%				30/30%			
40/40%				40/40%			

Table 2.11. CGM System between System Precision during Sleep Challenges (Sample Table)

Night Time (Y/N)	N Pairs	Gen 1 Tx (Study FW) PARD	Gen 2 Tx (Study FW) PARD	Gen 2 Tx (Updated FW) PARD
Y				
N

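### The concurrence tables have no CGM Low or High category, which inflates concurrence for YSI rows within 40-400 mg/dL and leaves no correct cell for YSI <40 or >400

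*SAP*

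**What the plan says.** SAP 6.3 sets the data rule: "All data will be used for the study safety and effectiveness analysis". SAP 6.4 forms pairs by "pairing each reference reading with the first Sensor reading that occurred up to 5 minutes after sample acquisition". Neither section says what happens when the device shows Low or High instead of a number.

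The only statement on this is a footnote in SAP Appendix 2, Table 2.9 (System Reliability), attached to the two cells that count matched CGM-YSI pairs: "Does not include data when the Systems displays High or Low Glucose".

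The concurrence tables report percentages of matched pairs. Tables 7A and 2.6 give the spread over CGM ranges within each YSI row. Tables 7B and 2.7 do the reverse, under the heading "Percent of Matched Pairs in Each YSI Glucose Range for Each CGM Glucose Range". The CGM categories are the nine from 40-60 to 351-400 (Protocol Tables 7A and 7B; SAP Tables 7B, 2.6B and 2.6C). The YSI rows of 7A and 2.6 include <40 and >400. Tables 6B and 6D also have no CGM row outside 40-400.

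SAP 6.10.1.9 to 6.10.1.11 give the system full scale as 40-400 mg/dL, and SAP 4.1.1 sets the effectiveness objective "for reference glucose values from 40-400 mg/dL". No section defines the Low and High displays, and no table counts them by YSI range.

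**The concern.** Concurrence asks whether the CGM category matches the YSI category. A Low or High display is a category, so the lack of a number is no reason to leave it out. Without a cell, two different results disappear:

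- A Low display when YSI is 55 is a misclassification, and it drops out of the 40-60 row.
- A Low display when YSI is 36 is correct, and it drops out of the <40 row.

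The first loss flatters the device and the second hides correct results. Both fall where the hypoglycemia and hyperglycemia challenges are meant to supply evidence. Protocol 5.12 states their purpose as evaluating the sensor over a wider range than would otherwise be seen.

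The comparison of three hardware/firmware configurations adds a further problem. Tables 2.2 to 2.5 have one shared column for the number of points, and Table 2.9 omits the Gen 2 transmitter with updated firmware. If one configuration shows Low or High more often, the tables would not reveal it.

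**Working it through.** **Plan's own figure.** Protocol 11.1.4 expects 22,786 paired points. Its range totals sum to 815 + 2194 + 5550 + 5303 + 3505 + 3052 + 1426 + 623 + 319 = 22,787, which agrees up to rounding. The lowest range (40-60) has 815 and the highest (350-400) has 319. Their share is (815 + 319) / 22,786 = 1134 / 22,786 = 5.0%.

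**Direction of the effect on concurrence.** For a YSI row inside 40-400, let *d* be the share of pairs displayed as Low or High and *c* the share of all pairs in the matching CGM category. A Low or High display cannot fall in the matching category of such a row. Dropping these pairs therefore leaves the numerator alone and gives

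reported concurrence = *c* / (1 - *d*),

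which exceeds *c* whenever *d* > 0. This needs no assumption about bias or error shape.

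**Size.** The documents give no sensor error distribution, so these are assumptions: YSI uniform within the row; normal error with zero bias; SD 8 or 12 mg/dL at 40-60 and CV 8% or 12% at 351-400; Low meaning <40 and High meaning >400; category edges at 60.5 and 350.5.

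| YSI row | Assumed error | *d* | *c* (Low/High counted) | *c*/(1 - *d*) (Low/High dropped) |
|---|---|---|---|---|
| 40-60 | SD 8 | 15.8% | 69.5% | 69.5/0.842 = 82.5% |
| 40-60 | SD 12 | 22.7% | 55.6% | 55.6/0.773 = 71.9% |
| 351-400 | CV 8% | 23.0% | 54.2% | 54.2/0.770 = 70.4% |
| 351-400 | CV 12% | 30.0% | 39.9% | 39.9/0.700 = 57.0% |

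Putting the lower edge at 60 instead of 60.5 lowers the 40-60 figures by 1 to 2 points. With bias at SD 8 in the 40-60 row, the pairs of figures (dropped versus counted) are 69% versus 64% at +5 mg/dL and 92% versus 63% at -5 mg/dL.

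Applied to the expected counts, this is roughly 815 × 0.158 = 129 to 815 × 0.227 = 185 pairs at the low end, and 319 × 0.230 = 73 to 319 × 0.300 = 96 at the high end. Neighbouring rows lose far less: about 1.0% at YSI 61-80 (SD 12) and 3.9% at 301-350 (CV 12%).

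**YSI <40 or >400.** The matching CGM category does not exist, so correct concurrence is 0% by layout. With YSI uniform on 20-40 and SD 12, 77.2% of pairs would vanish as Low. With YSI on 400-450 and CV 10%, 70.8% would vanish as High. Every pair left in these rows is a mismatch.

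**Tables 7B and 2.7.** Here the percentages are within CGM rows, so a missing Low or High row does not alter the rows shown. What is lost is how often a Low or High display was right.

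**Numeric agreement.** The same models, zero bias unless stated:

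| Case | Low/High dropped | Underlying values | Low/High set to 40/400 |
|---|---|---|---|
| YSI 40-60, SD 12: within 15 mg/dL | 85.3% | 78.9% | 86.8% |
| YSI 351-400, CV 12%: within 15% | 84.9% | 78.9% | 89.4% |
| YSI 351-400, CV 12%: MARD | 8.0% | 9.6% | 7.2% |
| YSI 40-60, SD 8, bias +5: within 15 mg/dL | 88.6% | 88.8% | not needed here |
| YSI 20-40, SD 12: within 15 mg/dL | 57.0% | 78.8% | not needed here |
| YSI 400-450, CV 10%: MARD | 11.2% | 8.0% | not needed here |

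Dropping these readings flatters agreement in some cases and worsens it in others. The sign depends on the YSI range, the bias and the value assigned to a Low or High display.

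**The case against.** The strongest reply is about scope. The footnote is attached only to a pair count in a reliability table. It is not attached to the MARD, agreement, error-grid, alert or concurrence tables. Low and High are not defined, and the shells are labelled as samples. A MARD cannot use a reading without a number, and the plan declares a 40-400 range for both the reference and the device. On that view this is an unstated measurement limit and no clear breach of SAP 6.3. One could also keep Low and High in the row totals of Table 7A and let the rows fall short of 100%, in which case concurrence would not be inflated.

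Much of this stands. The link from Table 2.9 to the other tables is an inference. It rests on the shared term matched pairs and on shells with nowhere to put these readings. If the row totals did include them, the shortfall would be unlabelled, so the missing cells would still need to be added.

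A reader might go further and infer that accuracy at the extremes is overstated in general. The documents do not support that. The direction for MARD and for agreement within 15/20 is not fixed. Substituting 40/400 makes zero-bias agreement look better than dropping does. At YSI <40 or >400 the omission works against the device.

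Tables 14A and 14B may capture part of the performance at the extremes through alert and detection rates, but SAP 6.10.1.16 does not say how Low and High displays enter them.

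**Conclusion.** The point holds for the concurrence tables. If their denominators are matched pairs as the Table 2.9 footnote counts them, concurrence in Tables 7A and 2.6 is overstated for every YSI row within 40-400 that has Low or High displays, chiefly 40-60 and 351-400. Under the assumed zero-bias errors the overstatement is about 13 to 17 points in each of these two rows. The direction follows from the layout; the size rests on the assumed SD and CV. For YSI <40 or >400, no correct concurrence can be shown.

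The finding does not extend to the effectiveness endpoint as a whole. The two end strata hold about 5% of expected pairs, so overall MARD should change little, and its direction is not determined. The study is descriptive and tests no hypothesis, so what is at stake is a fair description near 40 and 400 mg/dL and a fair comparison of the three configurations.

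**What to change.** - Add CGM columns for Low (<40) and High (>400) to Tables 7A and 2.6, and matching rows to Tables 7B and 2.7. Count these readings in the denominators, and define the two displays in the SAP.
- Report the number of Low and High displays by YSI range and by hardware/firmware configuration, including Gen 2 with updated firmware, beside Tables 6A-6D and 2.2-2.5.
- State in SAP 6.4 whether the Table 2.9 exclusion applies to the other accuracy tables.
- If Low and High are set to 40 and 400 for MARD or agreement, label it a sensitivity analysis and note that it can make numeric agreement look better.

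No new data are needed. The cost is a few extra table cells and less favourable concurrence at YSI 40-60 and 351-400. In return, the <40 and >400 rows can show correct results.
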